5.2. Primary Efficacy Composite Endpoint

The primary efficacy outcome variables (objectively confirmed – CEC Adjudicated) that will be used to define the primary efficacy composite endpoint are:

- symptomatic lower extremity proximal DVT
- asymptomatic lower extremity proximal DVT
- symptomatic lower extremity distal DVT
- symptomatic upper extremity DVT
- symptomatic non-fatal PE
- incidental PE and
- VTE-related death

5.2.1. Definition

The primary efficacy composite endpoint is defined as the time to the first occurrence of objectively confirmed symptomatic lower extremity proximal DVT, asymptomatic lower extremity proximal DVT, symptomatic lower extremity distal DVT, symptomatic upper extremity DVT, symptomatic non-fatal PE, incidental PE or VTE-related death as adjudicated by the independent Clinical Endpoint Committee (CEC).

5.2.2. Analysis Methods

The primary efficacy composite endpoint analysis will be based on the '**Up-to-Day 180' observation period for the ITT population** with censoring as defined in Section 2.6.

The cumulative distribution function of the time to first occurrence of the primary efficacy composite endpoint will be estimated by the Kaplan-Meier method. The primary statistical hypothesis will be tested using a log-rank test, stratified by tumor type (APC or non-APC).

The estimate of the hazard ratio (HR), RRR (RRR=100*[1-HR] %) and the 95% confidence intervals for the treatment effect will be provided based on a stratified Cox proportional hazard model (stratification factor: APC or non-APC) and including treatment group as a binary covariate (i.e., rivaroxaban, placebo).

The cumulative event rate derived from Kaplan-Meier estimate will also be displayed graphically to evaluate the timing of event occurrence and the consistency of the treatment effect over time.

5.2.2.1. Assessment of Proportional Hazards Assumption

The proportional hazards assumption in the primary efficacy time-to-event endpoint analysis based on the Cox-proportional hazard model will be assessed graphically using

- -log(-log) plots
- The goodness of fit testing approach as proposed by Harrell and Lee (1986)^{1,2}, a variation of a test originally proposed by Schoenfeld (1982)³ (Kleinbaum and Klein (2012)⁴ provide details on the implementation of this approach).

In the event of non-proportional hazards, alternative approaches will be used that include the Peto-Prentice test (Peto and Peto, 1972⁵; Prentice, 1978⁶) and Fleming-Harrington (1984⁷) test (with parameters for this test defined at p=1 and q=0). All tests will be performed with the use of SAS version 9.4 or higher (SAS Institute). Additional data explorations will be carried out to assess the non-proportionality of hazards between groups.

5.2.3. Supportive Analyses for Primary Efficacy Composite Endpoint

To assess the robustness of the conclusion of the primary analysis, supporting analyses of the primary efficacy composite endpoint will be performed based on different observation periods and analysis populations as described below with censoring rules defined in Section 2.6:

- Based on the '**On-Treatment**' **observation period** for the ITT population
- Based on the '**Up-to-Day 180**' **observation period** for the PP population
- Based on the '**On-Treatment**' **observation period** for the PP population
- Based on the '**Post-Randomization**' **observation period** for the ITT population
- Based on the '**Post-First Dose**' observation period for the ITT population

In all cases, the 2-sided 95% confidence interval (CI) for the hazard ratio (rivaroxaban vs placebo) will be provided using the stratified Cox proportional hazards model (stratification factor: APC or non-APC) and including treatment group as a binary covariate (i.e., rivaroxaban, placebo).

The cumulative event rate derived from Kaplan-Meier estimate will also be displayed graphically to evaluate the timing of event occurrence and the consistency of the treatment effect over time and tested using a log-rank test, stratified by tumor type (APC or non-APC).

Summary of Primary Efficacy Composite Endpoint Analysis Methods			
Endpoint	Observation Period	Analysis Population	Method
Primary Efficacy Composite Endpoint (CEC Adjudicated Events)	Primary Up-to-Day 180	ITT	Primary Analysis Kaplan-Meier Estimates (Cumulative event rates and stratified log-rank test) Cox-model (HR, 95% CI)
	Supportive On-Treatment	ITT	
	Up-to-Day 180	PP	
	On-Treatment	PP	
	Post-Randomization	ITT	
	Post-First Dose	ITT	
	Up-to-Day 180	ITT	Sensitivity Analysis 1. Include asymptomatic distal DVT 2. Dropout with no follow up – treating time to discontinuation as being time to an event.
	Up-to-Day 180	ITT	Competing Risk Analysis Deaths due to causes other than VTE-related will be a competing risk event Gray's 2-sample test (Cumulative Incidence Function) Fine and Gray regression model

5.2.4. Subgroup Analyses for the Primary Efficacy Composite Endpoint

Analyses of the primary efficacy composite endpoint will also be performed to examine the consistency of treatment effect across subgroups listed in Section 2.7. Homogeneity of treatment effect will be evaluated using the same model as described in Section 5.2.2 (stratified Cox proportional hazard model with treatment as a covariate). Subgroup analysis will be performed if there are at least 30 total randomized subjects in each subgroup category. Only descriptive

summaries will be presented for subgroups with fewer subjects. *The subgroup analysis by race and ethnicity will be denoted as 'Not Reported' for subjects from France as this information is not collected from the sites due to local regulation.*

The interaction of treatment with each of the subgroups will be analyzed based a stratified Cox proportional hazard model with stratification factor and treatment group with additional terms for subgroup and subgroup-by-treatment interaction. Further evaluations will be performed to assess and explain the nature of the interaction (qualitative or quantitative) if a significant (p value <0.10) interaction is observed. Significant interactions will be examined using a two-sided Gail-Simon⁸ test. Descriptive statistics (n, mean, standard deviation, median, and range) will be presented by treatment groups for each subgroup.

The subgroup analyses of the primary efficacy composite endpoint will be based on the '**Up-to-Day 180**' observation period for the ITT population with censoring as defined in Section 2.6.

5.2.5. Sensitivity Analyses

5.2.5.1. Additional Primary Efficacy Composite Endpoint – Include Asymptomatic Distal DVT

An additional composite efficacy endpoint will also be defined to *include the occurrences of 'asymptomatic lower extremity distal DVT'.*

Sensitivity analysis will be performed on the time to the first occurrence of objectively confirmed symptomatic lower extremity proximal DVT, asymptomatic lower extremity proximal DVT, symptomatic lower extremity distal DVT, asymptomatic lower extremity distal DVT, symptomatic upper extremity DVT, symptomatic non-fatal PE, incidental PE or VTE-related death as adjudicated by the independent Clinical Endpoint Committee (CEC). This analysis will be based on the ITT analysis population for the '**Up-to-Day 180**' observation period.

Cumulative distribution function of the time to first occurrence will be estimated by the Kaplan-Meier method and tested using a log-rank test, stratified by tumor type (APC or non-APC).

The estimate of the hazard ratio (HR), RRR (RRR=100*[1-HR] %) and the 95% confidence intervals for the treatment effect will be provided based on a stratified Cox proportional hazard model (stratification factor: APC or non-APC) and including treatment group as a binary covariate (i.e., rivaroxaban, placebo).

5.2.5.2. Sensitivity Analysis for Primary Efficacy Composite Endpoint

In this study, all data regarding occurrence of DVT, PE events and vital status (alive/dead) events will be collected for all subjects (completers and early withdrawal) at the Day 210/follow-up visit. Data for the primary efficacy composite endpoint will be missing for subjects for whom the Day 210/follow-up visit is not performed or if the visit was performed but the occurrence of an event was reported as unknown. A conservative approach will be used for subjects who withdrew from the double-blind period and did not have an event during the double-blind period.

In this approach, subjects who withdrew from the double-blind period for any reason other than death and were censored (i.e. had not experienced any VTE-related primary efficacy event during the double-blind period) and have missing or unknown Day210/follow up status will be considered as having a VTE-related event (i.e. not censored). The time from randomization to time of withdrawal will be assumed to be the time to an occurrence of a VTE-related primary efficacy composite event (no specific individual component will be assigned as the worst case).

The sensitivity analysis for the primary efficacy composite endpoint will be based on the '**Up-to-Day 180**' observation period for the ITT analysis population. For the above sensitivity analyses, the cumulative distribution function of the time to first occurrence will be estimated by the Kaplan-Meier method and tested using a log-rank test, stratified by tumor type (APC or non-APC).

The estimate of the hazard ratio (HR), RRR (RRR=100*[1-HR] %) and the 95% confidence intervals for the treatment effect will be provided based on a stratified Cox proportional hazard model (stratification factor: APC or non-APC) and including treatment group as a binary covariate (i.e., rivaroxaban, placebo).

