1.2. Study Design

[figure not shown]
This is a multicenter, randomized, double-blind, placebo-controlled, parallel-group, superiority study comparing the efficacy and safety of rivaroxaban with placebo for primary prophylaxis of VTE (defined as DVT and/or PE) in ambulatory adult men and women, 18 years of age and older, with various cancer types who are scheduled to initiate systemic cancer therapy as a component of their standard of care anticancer regimen, who have a baseline Khorana thromboembolic risk score of ≥ 2 , and are judged by the investigator or qualified designee to be an appropriate candidate for treatment with either placebo (10 mg orally once daily for 180 days) or rivaroxaban (10 mg orally once daily for 180 days) for thrombo-prophylaxis based on their clinical status.

The study consists of 3 periods: a 2-week screening period, a 180-day double-blind treatment period with an End-of-Treatment (EOT) visit [for subjects who permanently stop study drug], and a 30-day post-treatment follow-up period with a Day 210/End-of-Study (EOS) visit. The duration of participation in the study for each subject is approximately 32 weeks.

A target of approximately 700 subjects will be randomly assigned into the study in a 1:1 ratio to 1 of 2 treatment groups (rivaroxaban 10 mg qd and placebo) with approximately 350 subjects per treatment group. Towards the end of the enrollment phase, the planned total of subjects to be randomized into the study was revised to approximately 800 subjects due to a higher than originally anticipated subject discontinuation rate. In addition, subjects will be stratified at randomization by tumor type (APC or non-APC) such that approximately 25% of the subjects randomly assigned are those with APC.

Randomized subjects will continue with their recommended systemic cancer therapy (SCT) during the study period and will be examined by compression ultrasonography (CU) at every 8-week intervals. Subjects permanently discontinuing the study drug will be required to have a CU performed within 2 days of receiving their last dose of study drug.

Figure 1: Schematic Overview of the Study

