1.2.1. Study Drug Discontinuation and Early Withdrawal from Double-Blind Period

As per the protocol (Section 10.2.2), if a subject permanently discontinued study drug before the Day 180 visit/End of double-blind (EODB) period, this would not result in automatic permanent withdrawal of the subject from the study. Subjects are encouraged to make every effort to continue participation in the study and complete the schedule subsequent study visits until the planned end of their study double-blind duration (Day 180/EODB). All outcomes/events data (VTE, vital status (alive/dead), MI, stroke, and other thrombosis events) and safety data (including bleeding events) are collected. If a subject permanently discontinued study drug prior to Day 180 but continued in the study and completed all study visits up to Day 180, then this subject is considered as having ‘completed the double-blind period’ (that is, participated in the study up to the Day 180 visit).

All subjects including those who discontinued prior to Day 180 visit are contacted by telephone for a Day 210/EOS follow-up assessment. Any outcome/event data (including vital status) reported during this telephone visit is collected at this Day 210/EOS visit as agreed upon by the subject informed consent. In the event a subject withdrew consent or is lost-to-follow up, the vital status data are obtained through public information (death and other registries) per local guidelines and as allowed by local registration.

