In this study with a six-month planned treatment with rivaroxaban, the primary efficacy outcome variable is a composite of any symptomatic DVT, proximal asymptomatic DVT, any PE, and VTE-related death. The study design allows fixed treatment duration of 6 months on each successfully randomized subject. Assuming a cumulative incidence rate of 14.5% for the primary composite events in the placebo group and 6.0% cumulative incidence rate in the rivaroxaban treatment group, a total sample of about 700 randomized subjects (350 per treatment group) will be required to demonstrate approximately 60% relative risk reduction (RRR) in the primary efficacy composite endpoint with a 2-sided Type 1 error rate of 5% and >90% statistical power (calculation performed by EAST 6.3 software) assuming a 20% discontinuation rate. Towards the end of the enrollment phase, approximately 800 subjects were planned to be randomized into the study due to the high subject discontinuation rate. In addition, this sample size will allow for 80% statistical power in each stratum (APC or non-APC) for slightly larger differences in incidence rates between the two randomized treatment groups to be statistically significant.

Essentially, the above overall sample size estimate is calculated based on the following assumptions:

- Effect size: absolute difference in event rates = 8.5%, RRR = 58.6%
 - Primary efficacy composite endpoint event rate in the placebo arm: 14.5%
 - Primary efficacy composite endpoint event rate in the rivaroxaban arm: 6%
- Power: >90%
- Overall α level: 5%, 2-sided
- Probability of dropping out of the study: 20%
- Duration of enrollment period: 12 months
- Duration of study: 6 months (fixed for each randomized subject)

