4.2. Disposition Information

The number of subjects included in the analysis populations (ITT, PP and safety) and number of subjects who completed or withdrew from the double-blind period will be summarized by treatment group and stratification factor: APC or non-APC.

Summaries of reasons for withdrawal from the double-blind period and permanent discontinuation of treatment will be provided by treatment group.

Time to study drug discontinuation will be summarized by treatment group using the Kaplan-Meier method.

Time to early study discontinuation will also be summarized by treatment group using the Kaplan-Meier method.

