4.6. Study Drug Discontinuation and Early Withdrawal from Double-Blind Period

If a subject's study treatment must be permanently discontinued before the end of the double-blind treatment period, this will not result in automatic withdrawal of the subject from the study and they are encouraged to continue to be followed for efficacy and safety outcome until the end of the double-blind period/Day 180. Data from remaining scheduled visits are collected until the subject either completes the double-blind period/Day 180 visit or withdraws early from the study.

Outcome data for all subjects, those who completed the double-blind period as well as those who withdrew early from the double-blind period is also collected at the Day 210/EOS visit as agreed during the informed consent. Every effort will be made to follow-up the subject and collect the data including vital status. In the event a subject withdrew consent or is lost-to-follow up, the vital status data (dead/alive) will be obtained through public information (death and other registries) per local guidelines and as allowed by local registration.

Thus, there are two scenarios as described below:

1. Subject permanently discontinues study treatment but completes the double-blind period (i.e. completed the study/end of double-blind period)
 - a. If subject experiences an efficacy (primary or secondary) endpoint event at any time during the study (from randomization through double-blind period completion), then the event and corresponding time to the occurrence of the event will be included in the analysis of primary efficacy composite endpoint
 - b. If a subject has no efficacy composite endpoint event (primary or secondary) during the time in study, then this subject will be censored with the time to censoring defined as the time from randomization to last day of their complete assessment for study outcomes during the double-blind period [double-blind completion].
2. Subject permanently discontinues study treatment and withdraws early prior to the end of the double-blind period (i.e. withdrew from the study altogether) or dies during the double-blind period

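### The missing-outcome sensitivity analysis in SAP Section 5.2.5.2 counts unknown-status withdrawals as events in both arms. It is called conservative but is not reliably so, and no planned analysis varies the assumption by arm.

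*SAP*

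**What the plan says.** In the primary analysis, event-free subjects are censored at their last complete assessment (SAP Section 2.6.1). Section 5.2.5.2 then plans one analysis for missing outcomes, introduced with "A conservative approach will be used for subjects who withdrew from the double-blind period". It covers subjects who withdrew for a reason other than death and had no primary event. Of these, the ones who "have missing or unknown Day210/follow up status will be considered as having a VTE-related event (i.e. not censored"), with the withdrawal date as the event date. Treatment arm is not mentioned, so the rule applies to both arms. The summary table in Section 5.2.3 gives it in short form: "treating time to discontinuation as being time to an event".

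The other planned analyses of the primary endpoint do something else:
- Section 5.2.3 changes the observation period or the population.
- Section 5.2.5.1 adds asymptomatic distal DVT.
- Section 5.3 treats non-VTE death as a competing risk.

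Several provisions bear on how often status will be unknown:
- Section 1.2.1: "All subjects including those who discontinued prior to Day 180 visit are contacted by telephone for a Day 210/EOS follow-up assessment".
- Section 4.6 says that outcome data for "those who withdrew early from the double-blind period is also collected at the Day 210/EOS visit".
- Section 4.2: "Time to early study discontinuation will also be summarized by treatment group using the Kaplan-Meier method".
- Section 1.4 assumes 20% dropout with no split by arm. Section 1.2 reports that the sample size was "revised to approximately 800 subjects due to a higher than originally anticipated subject discontinuation rate".

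**The concern.** A missing-outcome analysis is conservative if it leans against the claim being tested. Counting unknown-status withdrawals as events only in the rivaroxaban arm would always do so. Counting them in both arms changes the endpoint to VTE or unknown-status loss, and the comparison then blends the treatment effect on VTE with any difference in loss. If placebo loses more subjects, the imputed events count for rivaroxaban.

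The stake is how far the robustness claim can be trusted. This is the only analysis that addresses unknown outcomes, in a trial enlarged because discontinuation was high. If it agrees with the primary result, a reader of the SAP will take that as a hard test passed. The label does not guarantee this.

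**Working it through.** **Inputs.** From SAP Section 1.4: 14.5% versus 6.0% at six months, two-sided 5%, power above 90%, 20% dropout, about 700 subjects, later about 800 (400 per arm). The SAP gives no unknown-status rates by arm, so every loss rate below is an assumption.

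**The plan's own figure.** HR = ln(0.94)/ln(0.855) = 0.395. Freedman's formula at 90% power: 10.51 × (1.395/0.605)² = 56 events. The mean event rate is 10.25%, so 56/0.1025 = 546 subjects, and 546/0.8 = 683. This agrees with about 700. With 280 evaluable per arm, power is 91.5% (two proportions) or 94.0% (Schoenfeld).

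**Model for the rule.** Independent exponential times to VTE (hazard λ) and to unknown-status withdrawal (hazard δ), both per 180 days, 400 per arm, no strata. Withdrawals with known status are not modelled.
- λ = −ln(1 − event rate): placebo 0.1567, rivaroxaban 0.0619.
- δ = −ln(1 − loss rate): 10% gives 0.1054, 5% gives 0.0513.
- HR under the rule = (λ + δ, rivaroxaban)/(λ + δ, placebo).
- Expected z ≈ (√events/2) × ln HR. Negative values favour rivaroxaban.

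**Equal loss, planned effect.** The rule works against the drug.

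| Loss in each arm | HR under the rule | Significant in favour (simulated) |
|---|---|---|
| 3% | 0.49 | 94% |
| 5% | 0.54 | 91% |
| 10% | 0.64 | 79% |
| 20% | 0.75 | 57% |

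The primary analysis has HR 0.395 and is significant in 97–98%. If rivaroxaban loses more (20% versus 10% on placebo), the HR under the rule is 1.09.

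**More placebo loss, planned effect, 10% versus 5%.**
- HR = (0.0619 + 0.0513)/(0.1567 + 0.1054) = 0.43, nearer to 1 than 0.395.
- Primary events: 55.1 + 23.4 = 78.5, so z ≈ (√78.5/2) × ln 0.395 = −4.1.
- Events under the rule: 92.2 + 42.8 = 135.0, so z ≈ (√135.0/2) × ln 0.432 = −4.9.
- Simulated mean z moves from −3.9 to −4.7.

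The HR weakens while the evidence strengthens. At 20% versus 10% the HR goes from 0.395 to 0.44 and the formula z from −4.02 to −5.62.

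**Two boundaries at 10% placebo loss, planned effect.**
- HR below its true value: needs rivaroxaban δ < 0.395 × 0.1054 = 0.0416, a loss under 4.1%.
- Stronger z: at 6% rivaroxaban loss, HR 0.472 with 138.8 events gives z ≈ −4.42 against −4.11 in the primary. At 7%, HR 0.513 with 142.5 events gives −3.98 against −4.11. The formula crosses just below 7%; simulation puts it at about 7%.

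**Weaker effects** (placebo versus rivaroxaban loss; simulated share significant in favour):

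| Loss | 14.5% vs 10.5%: HR (true 0.71) | Share (primary 38–40%) | No effect: HR | Share (primary 2.5%) |
|---|---|---|---|---|
| 3% vs 2% | 0.70 | 48% | 0.945 | 5% |
| 5% vs 3% | 0.68 | 57% | 0.90 | 9% |
| 10% vs 5% | 0.62 | 83% | 0.79 | 32% |

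If true loss is equal, splits at least this large in rivaroxaban's favour arise by chance in about 18%, 7% and 0.4% of trials (one-sided normal approximation). The large distortions therefore need a real difference in loss.

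**The case against.** The other side has a good case on consequence.

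- **At the planned effect the rule usually pulls the HR toward 1, and the SAP suggests no imbalance in loss.** True of the HR. It does not settle the matter, because z can strengthen well before the HR boundary is reached.
- **Losing significance under equal loss is what a conservative check does.** This stands. The equal-loss results show the rule being conservative and are not evidence against the label.
- **The simulated losses are non-informative.** This also stands. The no-effect wins are chance results, not bias from missing data, and a reader should not take 32% as a false-positive rate of the trial. The figures show how the rule behaves. They do not measure the harm from informative loss, which was not computed.
- **Unknown status may be rare.** Only event-free withdrawals with unknown Day 210 status are imputed. Every subject is to be telephoned, and events after withdrawal but before Day 180 count in the primary analysis (Section 4.6). Treating the whole 20% dropout as unknown would be an upper bound only.
- **The imputation can be reconstructed.** Events under the rule minus primary events, by arm, give the number imputed. Direct counts would be simpler, and they still would not show how far the result depends on the assumption in one arm.
- **A tipping-point analysis is not stricter at every delta.** With 3% versus 2% loss and no effect, it keeps 93% of chance wins at delta 1, where the both-arms rule keeps 86%. Its value is that it reports where the conclusion changes. Which delta is plausible remains a judgement.

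**Conclusion.** The point holds in a limited form. The both-arms rule is conservative when unknown-status loss is equal or higher on rivaroxaban. When placebo loses more, it can strengthen the evidence for the drug, even with an HR nearer to 1. At the planned effect and 10% placebo loss, this starts below about 7% rivaroxaban loss. The label therefore promises something that depends on data not yet seen, and no other planned analysis varies the unknown outcome by arm.

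These sizes rest on constant hazards, independent loss, 400 per arm, no stratification and assumed loss rates. At 3% versus 2% the distortion is small.

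Two stronger readings are tempting. One is that the rule biases the trial's main result or its type I error. It does not: the analysis lies outside the testing hierarchy in Section 5.5. The other is that the rule favours rivaroxaban in general. It does not, as the equal-loss results show. The weakness is confined to a robustness check. It merits a change because the remedy is cheap and uses data already collected.

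**What to change.** In Section 5.2.5.2:
1. Delete the word conservative and keep the both-arms rule as a descriptive analysis.
2. Report the number of unknown-status withdrawals by arm.
3. Add one arm-specific multiple-imputation tipping-point analysis. For each unknown-status withdrawal, impute time to VTE from withdrawal to Day 180. Use the placebo hazard for placebo subjects and delta times the placebo hazard for rivaroxaban subjects. Fit the stratified Cox model of Section 5.2.2 and combine by Rubin's rules.
4. Raise delta from 1 to the limit at which every unknown-status rivaroxaban subject has an event at withdrawal. Report the delta at which significance is lost, or state that there is none up to the limit.

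The range should not stop early. In 1,500 simulated trials at the planned effect with equal loss of 3%, 5%, 10% or 20%, 97%, 95%, 86% and 49% were still significant at delta 3. At the limit the shares were 71%, 36%, 1% and 0%. The limit alone is therefore too severe to be informative when loss is 10% or more, and the delta at which significance is lost is the useful result.

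The cost is SAP wording, modest programming and one more sensitivity table. No new data are needed.
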